## 1. Summary

Hypertension is a rapidly increasing health concern in Africa. Hypertension begins in childhood and contributes to early development of cardiovascular disease (CVD). High blood pressure in childhood is most commonly “essential hypertension” (has no specific identifiable cause) and in most cases in children it remains undiagnosed. Identifying and successfully managing children with high blood pressure may have important benefits for long term CVD outcomes.

The association between birth weight and blood pressure has been intensively studied in affluent countries but not in low-income settings. Our key goal is to investigate whether birth weight and pre- and peri-natal exposures are important in programming blood pressure in children in Uganda. In addition, we will assess the relationship between such exposures and other biomarkers of metabolic processes and CVD risk. Also, DNA archive and genetic data are already available for the cohort and this will allow us to analyse associations between genetic polymorphisms and blood pressure, and between genetic polymorphisms and biomarkers of CVD risk, in this population.

The existence of the Entebbe Mother and Baby Study (EMaBS) birth cohort offers a unique opportunity to investigate these associations, providing information on the likely aetiology of high blood pressure and of metabolic disorders, and enabling the generation of strategies for prevention and management

of cardiovascular disease for this population, and for similar settings. This study will be conducted among 10 and 11 year old children under follow up in the EMaBS.

## **2. Background**

Hypertension is a major public health burden globally, and a rapidly growing one in Sub-Saharan Africa where at least 79 million people are believed to be affected (1). Overall, the prevalence of hypertension in Africa is estimated to range from 6 to 48% (2) but there is little or no reliable data on the prevalence of Non Communicable Diseases (NCD) and their associated risk factors in Africa (2-4). There is little attention to the prevention and management of hypertension in Uganda and similar countries in SSA, and, until recently, this has not been considered a public health priority.

The majority of the people affected by hypertension are unaware of it, and of those that are aware, many are not on treatment (4-6). Poor healthcare provision and late detection remain major obstacles to preventing and controlling hypertension in Sub Saharan Africa SSA (6). Studies in Uganda have shown a prevalence of hypertension of 22.5% in adults in rural Uganda (7) and of 28% among HIV-positive individuals on antiretroviral therapy(8), comparable to the prevalence of hypertension in developed countries (9, 10). Based on a United States normogram (11) (since local standards are not available) our pilot study in Wakiso District found blood pressure above the 95th centile in 17% of school children on the first reading. Despite the evidence of a growing burden of hypertension in SSA, much remains to be done to determine the extent of the problem, especially in children.

### *High blood pressure in childhood is a risk factor for adult hypertension*

Hypertension, which contributes to cardiovascular disease, mortality and morbidity in adulthood (12-16), has its origins in childhood (17-19). Children with high blood pressure tend to be hypertensive adults (20). Despite this knowledge, very little attention has been paid to the problem of high blood pressure in children and adolescents, especially in developing countries.

### *Risk factors for hypertension and cardiovascular disease in developed countries*

In developed countries, high blood pressure is linked to low birth weight (21-25), prematurity (26), body mass index (BMI) (16, 27-29) gender (29, 30), ethnicity (30) and waist circumference (WC) (28). Also, among low birth weight infants, accelerated weight gain is associated with elevated blood pressure (21-23, 31). Other important biomarkers for cardiovascular disease risk – for example elevated blood

glucose, elevated triglycerides, reduced high density Lipids (HDL) cholesterol – are often associated with high blood pressure in the metabolic syndrome (24, 32). Also, there is increasing evidence of a link between the metabolic syndrome and chronic, low-grade inflammation, assessed (for example) by circulating C-reactive protein (CRP) levels. C-reactive protein levels show additive effects for cardiovascular disease over and above the metabolic risk factors (32).

*Risk factors for high blood pressure and cardiovascular disease risk factors in childhood in Africa*

Data on risk factors for high blood pressure in childhood in Africa are very limited (33-35). In Ghana, increased body mass index (BMI) and urbanisation were risk factors for high blood pressure among school children (35). Low socio-economic status was linked to elevated blood pressure in Kinshasa (34). However, these studies were based on a single blood pressure reading, giving limited accuracy.

Other risk factors for cardiovascular disease may be strongly influenced by environmental factors in our setting. For example, CRP levels in adults – noted above as a marker of low grade inflammation and CVD risk - have been shown to be markedly lower among adults in rural Ecuador, or in the Philippines, when compared with adults in the United States, and there is evidence that this may be related to immunomodulation resulting from early-life infectious exposures (36). Similarly, there is recent evidence from animal models that helminth infections may influence glucose metabolism through their impact on the immune system: eosinophils, which are strongly induced by helminth infections, seem to influence macrophages in adipose tissue to adopt an anti-inflammatory profile, resulting in reduced insulin resistance and improved glucose tolerance (37). The Entebbe Mother and Baby Study, with its detailed data on helminth infections and their treatment, offers a unique opportunity to investigate whether helminth exposure in early life influences metabolic parameters, including CVD risk factors, in humans.

*Relationship between birth weight and blood pressure in Africa*

Among populations of African descent, the association between birth weight and blood pressure is not certain (38). In Soweto, South Africa (39), and Harare, Zimbabwe (40), birth weight was inversely associated with systolic blood pressure among school children. But in rural Gambia, birth weight was not associated with blood pressure (41). This could be because the causes of low birth weight differ between rural, tropical Africa and developed or sub-tropical settings: for example, malaria is an important cause of low birth weight which is restricted to the tropics (42). Alternatively, effects of the prenatal exposures associated with low birth weight may be modified by environmental factors in

infancy. In order to understand the conflicting results from studies described, there is a need to investigate effects of birth weight on blood pressure in an African setting, with heavy exposure to parasitic and other infectious diseases. The epidemiology of hypertension in tropical Africa may be different to that in the industrialised countries.

*Genetics of hypertension and cardiovascular disease risk*

Besides environmental influences, there is strong evidence that genetic traits contribute to hypertension (43). Meta-analyses of studies in Europeans and East Asians have identified single nucleotide polymorphisms related to the serine/threonine kinase 39 (STK39) gene and hypertension. However, these findings have not been replicated among people of African descent (44).

Genetic studies of complex traits in African subjects are important. Because African populations are older, genetic diversity is higher, and linkage disequilibrium (the tendency for groups of genes to be inherited together) is lower, among Africans than among Caucasians. Also, selection pressure driven by exposure to infections differs between these populations, exemplified by the striking observation that mutations in the apolipoprotein L1 gene in African Americans both protect against infection with *Trypanosoma brucei rhodesiense* and associate with an increased risk of developing renal glomerulosclerosis and hypertension (45).

Studies among African populations therefore have the potential to provide unique insights into genetic mechanisms behind human health and disease. Currently, an on-going study in Kyamulibwa, South West Uganda, a collaboration between the MRC/UVRI Unit and the Wellcome Trust Sanger Institute, is investigating genetic factors associated with hypertension and metabolic markers of cardiovascular disease risk among more than 5000 participants from a rural Ugandan population. At the same time, under the already-approved EMaBS amendment, Appendix 13 (“The genetics of response to vaccination, infectious and inflammatory disease in the children from the Entebbe Mother and Baby Study”) a genome-wide genetic analysis is being conducted at the Sanger Institute for samples from EMaBS, as part of a collaboration with the University of Oxford. This provides the opportunity for us now to examine genetic associations with blood pressure and biomarkers of CVD risk in EMaBS, and also to relate our findings to the results from the Kyamulibwa study.

*Blood pressure and biomarkers of cardiovascular disease risk in the EMaBS*

Within EMaBS, we now, therefore plan to investigate the influence of birth weight, of pre- and peri-natal exposures and of genetic polymorphisms, on blood pressure and on metabolic parameters, particularly those associated with CVD risk, at school age in a birth cohort in the tropics. The EMaBS birth cohort represents a unique opportunity to investigate these associations among Ugandan children aged 10 and 11 years. Data on birth weight and on infectious exposures has been collected since pregnancy, through labour, delivery, infancy to childhood. This will help us to understand whether birth weight and pre- and peri-natal exposures are important in programming blood pressure and CVD risk factors among African children.

### **3. Rationale for the study**

Little or no research has been conducted on childhood blood pressure in Uganda and it is likely that hypertension will be an increasing health problem as a result of the societal transition. This work is one of a number of studies on blood pressure and on the metabolic syndrome that the MRC/UVRI hopes to conduct over the forthcoming years in Uganda.

EMaBS is one of the few birth cohorts that have been established in tropical Africa. It offers a unique opportunity to study the influence on blood pressure at school age of birth weight, and of pre- and peri-natal exposures, in the tropics. In addition, genetic data are being generated for cohort members under an approved, earlier, protocol amendment and will be available to allow analysis of genetic markers associated with blood pressure in this population.

The existence of data from this large birth cohort of mothers and babies is a rare opportunity to investigate the influence of birth weight, and of pre- and peri-natal exposures, on blood pressure at school age in the tropics. Identifying and successfully treating children with high blood pressure may have an important impact on long term CVD outcomes. This is a society in transition and this work will allow us to inform the Ministry of Health on the burden of high blood pressure at an early age. Understanding the risk factors for hypertension will be essential in mitigating the effects of this burgeoning epidemic, and will provide data for formulating evidence-based health policy and interventions. This may have global implications in terms of the design of interventions against hypertension and cardiovascular disease.

## **4. Hypothesis**

The fetal origin hypothesis proposes that intra uterine nutrition and growth, of which birth weight is a key marker, are vital in programming blood pressure in later life. The rapid growth hypothesis suggests that the adverse effects of low birth weight are further strengthened by a rapid increase in weight after birth, and that this, too, influences blood pressures in later life. These risk factors have been intensively studied in affluent countries but not in low-income settings, where infectious diseases are the leading cause of morbidity and mortality, including low birth weight. However the burden of non-communicable diseases and of hypertension in particular, is rapidly growing in Africa, while the continent is ill-equipped to address this burden. We will address the hypothesis that birth weight and pre- and peri-natal infectious exposures are important in programming blood pressure and metabolic factors associated with cardiovascular disease risk among children in the tropics.

## **5. Objectives**

The key goal is to investigate whether birth weight and other pre- and peri-natal exposures are important in programming blood pressure in children

### **5.1. Specific objectives**

- 5.1.1. To determine whether there is an association between birth weight and blood pressure among 10 and 11 year old children in EMaBS.
- 5.1.2. To identify other early life exposures associated with blood pressure among 10 and 11 year old children in EMaBS.
- 5.1.3. To investigate whether the same exposures are associated with metabolic parameters linked to CVD risk among 10 and 11 year old children in EMaBS.
- 5.1.4. To investigate whether genetic polymorphisms are associated with blood pressure and with metabolic parameters linked to CVD risk among 10 and 11 year old children in EMaBS.

## 6. Methods

### 6.1. Study design

This is a longitudinal study that will take advantage of the already existing EMaBS birth cohort under follow up in Entebbe Uganda. The study will be conducted in Entebbe at the EMaBS study clinic and in the MRC/UVRI Laboratories. The participant data collected at the 10 or 11 year old study visit will be linked to earlier individual data that has been collected from pregnancy through delivery to date, and to genetic data that has been obtained through a previously-approved EMaBS protocol amendment.

### 6.2. Study area and participants

This study will be conducted among the current EMaBS participants. Briefly, the EMABS is located on the Entebbe peninsula in Uganda, an area occupied by peri-urban, rural, and fishing communities. In total, 2507 pregnant women were enrolled and 2345 live births were recorded (46, 47). There are 1964 (82 %) children for whom birth weight is available (46) and 1622 (69%) children were seen at age 5 years (48). We continue to see over 1000 children for routine follow up visits per year.

Children aged 10 or 11 years of age who are currently under follow up in the EMaBS birth cohort will be invited to enrol into this study. They will be included in the study at routine annual visits if they are well, in the opinion of the study physician and if written, informed consent is provided by the parent or guardian, and written, informed assent is provided by the child. Children who are unwell will be treated for current illness and invited to return for the blood pressure assessment when they have recovered. Children will be excluded from this assessment if consent and assent for it are not given.

### 6.3. Outcome measures

- 6.3.1. **The primary outcomes will be systolic and diastolic blood pressure at age 10-11 years.** This age range has been chosen to allow all active cohort participants to be seen within a two-year period between early 2014 and early 2016. This is the period for which funding for this study is available.
- 6.3.2. **Secondary outcomes will be lipid profiles, glycosylated haemoglobin A1c (HbA1c) and CRP levels measured in a random (i.e. non-fasting) blood sample at age 10-11 years.** Lipid profiles will include total cholesterol and high density lipoprotein (HDL)

levels. HbA1c measurement will provide an estimate of integrated plasma glycaemia for the previous 2-3 month (49, 50). CRP will be measured to assess chronic inflammation. If funds permit, CRP will be assessed not only at 10/11 years, but also in plasma or serum samples stored at annual visits from age one to nine years, for exploratory analyses investigating the hypothesis that patterns of chronic, low-grade inflammation are established early in life. In addition, a sample of urine and a sample of plasma or serum will be stored for investigation using “metabolomics”(see below) if additional funding for this can be secured.

## 6.4. Exposures

6.4.1. Birth weight (grams) will be the main exposure

Other exposures considered will include the following:

6.4.2. Child’s gender, and age at the time of blood pressure assessment

6.4.3. Household and family risk factors (socio-economic status, environmental factors in the home, location of residence, parental education, tribe, sleep, family history of high blood pressure, heart disease and stroke.)

6.4.4. Life-course exposures (prenatal exposure to maternal helminth infections and their treatment, and other infections during pregnancy; helminth infections and treatment, and other infectious disease episodes during infancy; childhood, length and head circumference at birth, weight and height trajectory during infancy and childhood)

6.4.5. Current anthropometric parameters: height, weight and waist circumference

6.4.6. Genetic markers

## 6.5. Study procedures

Provisions of the existing EMaBS protocol include routine annual visits at which a questionnaire is completed, weight and height are measured, a stool sample is obtained and albendazole treatment is provided as a routine to all participants. The additional procedures required for this blood pressure study will be conducted alongside the already-approved procedures. Parents or guardians are often contacted before the visit, to remind them to attend, and for this visit they will be asked to bring the child in the morning, fasting, if possible.

After explaining the procedures for the blood pressure study (BPS) and obtaining consent and assent for the additional BPS procedures, anthropometric measurements for height, weight and the waist circumference (WC) will be taken when the child is wearing light clothing. The WC will be measured at the mid-way position between the lowest rib and the iliac crest and recorded to the nearest 0.1 cm. The weight will be measured to the nearest 1 kg and height at the nearest 0.1 cm. A study questionnaire will be completed by the study investigator with the help of the parent or guardian. The time since food or drink was last taken will be recorded.

The child will be asked to sit and rest for at least five minutes. Then systolic and diastolic blood pressure will be measured using the appropriate cuff size for the arm circumference (51). Three readings will be taken five minutes apart. The average blood pressure reading for that visit will be compared with international normograms (52), for gender by age and height percentile (Appendix 1). A child with an average blood pressure  $\geq 95^{\text{th}}$  centile based on their gender, age and height percentile will be invited for two more visits on different days for additional blood pressure measurement. Hypertension is defined as an average systolic and or/ diastolic blood pressure that is  $\geq 95^{\text{th}}$  percentile for gender, age and height on three separate occasions (51, 52). The height percentile will be determined using the standard growth chart (51).

Blood tubes will be labelled with a unique identification number and date of collection, linking the sample to the individual child data already collected. The total volume of blood collected will be 14 mls: 6mls of blood will be collected in an EDTA tube, 4mls in the fluoride oxalate tube and 4 mls in a serum tube, from each child on the first visit. From the EDTA tube, a blood smear for malaria parasites will be made and read and 2mls will be removed for measurement of Full Blood Count (FBC) and for investigation for *M. perstans* infection. Blood will be aliquoted into labelled microtubes and stored at  $-80^{\circ}\text{C}$  for later measurement for glycosylated haemoglobin (HbA1c). Serum samples will be stored for measurement of urea and electrolytes among children found to have high blood pressure, and for lipid profile and CRP. The 4mls in the fluoride oxalate tube will be used to measure fasting/random blood sugars. After the blood sample has been taken the children will be provided with refreshments such as juice, biscuits, fruit.

High blood pressure will be categorised according to the extent to which a child's blood pressure exceeds the 95th centile (51). Children with hypertension will be investigated for serum urea and electrolytes and glomerular filtration rate, urine dipstick for proteinuria, renal ultrasound, chest x-ray,

electrocardiogram and echocardiogram. They will be managed for hypertension in consultation with a paediatric blood pressure specialist, [name] (collaborator) at Mulago Hospital.

Measurement of blood pressure will be introduced as part of the annual visit routine for all children aged above 10/11 years. This will allow monitoring of those with pressures that are elevated but to a lesser degree.

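### Weight at the 10/11-year visit is recorded only to the nearest 1 kg, which adds a small, avoidable rounding error to a listed exposure

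*Protocol*

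**What the plan says.** Protocol section 6.5 fixes the resolution of the three body measurements at the 10/11-year visit. For weight and height it says: "The weight will be measured to the nearest 1 kg and height at the nearest 0.1 cm". Waist circumference is "recorded to the nearest 0.1 cm".

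Weight enters the exposures in two places. Section 6.4.5 lists "Current anthropometric parameters: height, weight and waist circumference". Section 6.4.4 includes "weight and height trajectory during infancy and childhood" among the life-course exposures. The rapid-growth idea in section 4 is that "the adverse effects of low birth weight are further strengthened by a rapid increase in weight after birth".

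The earlier weights come from the parent cohort. Section 6.5 states: "Provisions of the existing EMaBS protocol include routine annual visits at which a questionnaire is completed, weight and height are measured". The protocol does not say how finely those weights were recorded. Section 6.4.1 is explicit about the primary exposure: "Birth weight (grams) will be the main exposure".

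**The concern.** A 1 kg step is coarse beside the 0.1 cm used for height and waist. For a child of about 30 kg (an assumption), it is about 3% of body weight. Rounding of this kind acts much like random measurement error: it pulls a simple regression slope towards zero and costs some power. It also discards information for good, because a weight written as a whole number of kilograms cannot be refined after data collection.

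The size of the loss depends on which weight variable is analysed. Rounding matters little against the wide spread of attained weight among 10- and 11-year-olds. It matters more against the narrower spread of a weight change over a short interval. The protocol gives no reason for the coarser step.

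**Working it through.** **The plan's own figure.** The sample-size section assumes 1000 children, 8% of low birth weight (80 against 920), SDs of 12 and 8 mmHg, and p = 0.05, taken here as two-sided.
- Standard-error factor: √(1/80 + 1/920) = 0.1166.
- Systolic: 4 / (12 × 0.1166) = 2.86, so power = Φ(2.86 − 1.96) = 81.6%. The protocol states over 80%.
- Diastolic: 3 / (8 × 0.1166) = 3.22, so power = Φ(3.22 − 1.96) = 89.6%. The protocol states nearly 90%.

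Both reproduce. Neither uses weight at age 10/11, so the rounding rule leaves them unchanged.

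**Rounding error.** A step of 1 kg gives an error of at most 0.5 kg, close to uniform, with SD 1/√12 = 0.289 kg and variance 0.083 kg². A simulation of one million weights (mean 30 kg, SD 5 kg, both assumed) gave an error SD of 0.2886 kg and a squared correlation of 0.9967 between true and rounded weight, in line with the formula below.

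**Share of the slope retained** in a simple regression: SD² / (SD² + error variance). Every SD and height below is an assumption, because the protocol gives none.

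| Variable | Assumed spread | Retained at 1 kg |
|---|---|---|
| Current weight | SD 3 to 7 kg | 0.991 to 0.998 |
| BMI, height 1.35 m | SD 1.5 to 2.0 kg/m² | 0.989 to 0.994 |
| One-year gain, last weight rounded | SD 0.8 / 1.0 / 1.5 kg | 0.885 / 0.923 / 0.964 |
| One-year gain, both weights rounded | SD 0.8 / 1.0 / 1.5 kg | 0.793 / 0.857 / 0.931 |

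- *Current weight*, SD 3 kg: 9 / (9 + 0.083) = 0.991.
- *Gain since birth*: birth weight is in grams, so only the final weight carries the 1 kg rounding. The loss is about that for current weight, under 1%.
- *BMI*: the error SD is 0.289 / 1.35² = 0.158 kg/m². Rounding height to 0.1 cm contributes about (2 × 16 / 1.35) × 0.001/√12 = 0.007 kg/m² at an assumed BMI of 16, so weight rounding dominates by a factor of about 20. Over heights of 1.25 to 1.45 m and SDs of 1.5 to 3 kg/m², the share retained is 0.985 to 0.998.
- *One-year gain*, SD 0.8 kg, last weight rounded: 0.64 / (0.64 + 0.083) = 0.885. With both rounded: 0.64 / (0.64 + 0.167) = 0.793.

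**Power.** Take a continuous exposure with 80% power when error-free (non-centrality 1.96 + 0.84 = 2.80) and multiply the non-centrality by the square root of the share retained.
- At 0.985, the lowest value for weight or BMI, power is 79.4%.
- At 0.923 (one-year gain, SD 1.0 kg, last weight rounded), power is 76.8%.
- At 0.793 (SD 0.8 kg, both rounded), power is about 70%.

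**With a 0.1 kg step.** The error SD falls to 0.029 kg. The share retained rises to at least 0.9999 for weight, 0.9998 for BMI, and 0.997 for one-year gain even with both weights recorded at that step.

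**The case against.** The strongest reply is that almost nothing the protocol names is materially harmed. Current weight loses under 1%. BMI appears in the Background as a risk factor, but section 6.4 and the analysis plan do not list it. A one-year gain ending at age 10/11 is not a named exposure, so the 4% to 12% describes a variable the plan may never use. All of this stands, and it is why the point is small.

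A reader might infer that the rule undermines the test of the rapid-growth hypothesis. The protocol does not support that. The hypothesis concerns weight gain after birth, and the trajectory runs through infancy and childhood. Those weights come mainly from earlier cohort visits, whose resolution is not given. The 1 kg rule is stated only for the 10/11-year visit, so only the last point of the trajectory is known to be rounded. For the same reason, the losses with both weights rounded (about 7% to 21%) are conditional and not established.

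It is also fair to say that attenuation is the expected direction only for a single mismeasured exposure. Where current weight is an adjustment variable in a multiple regression, its error leaves some residual confounding, whose direction is not fixed.

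Finally, the 1 kg may be a slip, and the scale, the CRF and the planned SOPs are not shown. That does not remove the point: the written rule is what staff would follow, and if it is a slip it still needs correcting.

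**Conclusion.** The point holds as a minor improvement. The 1 kg rule in section 6.5 discards information on a listed exposure and on the last point of the weight trajectory. Rounding error with SD 0.29 kg costs under 1% of the slope for current weight and for gain since birth, and about 1% for a derived BMI (1.5% in the least favourable case considered). Only a short-interval gain ending at this visit would lose more: about 4% to 12% over one year with this weight alone rounded.

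These percentages rest on assumed SDs and heights and on simple regression. The 12% belongs to the smallest gain SD considered, 0.8 kg. Birth weight, the blood pressure outcomes, the centile classification by gender, age and height, and the stated power do not depend on this weight.

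**What to change.** In section 6.5, change the weight resolution from the nearest 1 kg to the nearest 0.1 kg, or to the finest division of the clinic scale if it reads more coarsely. Give the CRF weight field the matching decimal place.

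The children are already weighed at this visit, so no procedure is added. The cost is one figure in the protocol and one decimal on the form.
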